3.2.2 Expansion cohorts

- Analyses will be conducted separately for sarcoma and ovarian cancer patients.
- Primary efficacy endpoint will be analysed based on the eligible and assessable population:
 - Each patient will be assigned one of the following categories:
 - Complete response
 - Partial response
 - Stable disease
 - Progression
 - Inevaluable for response
 - The rate of objective response (complete or partial response) under treatment will be reported:
 - All eligible and assessable patients will be included in the denominator for the calculation of the objective response rate (ORR).
 - The 95% two-sided confidence limits will be provided for the ORR (binomial law).
 - First endpoint conclusions will be based on the objective response rate ORR for all eligible and assessable patients (section 10.2) after centralized radiological review of the data.
- As regards to the other efficacy endpoints, the analyses will be carried out in the eligible and assessable population:
 - Each patient will be assigned one of the following categories:
 - Complete response
 - Partial response
 - Stable disease
 - Progression
 - Inevaluable for response
 - The rate of best overall response will be calculated as the number of patients alive with the best response (recorded from the start of the treatment) divided by the number of patients eligible and assessable.
 - The 6-month progression-free rate will be calculated as the number of patients remaining alive and progression-free at 6 months from the start of the treatment divided by the number of patients eligible and assessable.
 - The 6-month objective response rate will be calculated as the number of patients alive with complete or partial response at 6 months divided by the number of patients eligible and assessable.
 - The 95% two-sided confidence limits will be provided for the calculated rates (binomial law)
- The safety analysis will be performed on the safety population.
- Quantitative variables will be described using mean and standard deviations if the normality assumption is satisfied, else other descriptive statistics (median, range, quartiles) will be reported.
- Qualitative variables will be described using frequency, percentage and 95% confidence interval (binomial law).
- Survival endpoints will be analysed using the Kaplan-Meier method. The median survival rates will be reported with a 95% confidence interval. Median follow-up will be calculated using the reverse Kaplan-Meier method.

3.2.3 Primary endpoint

- Dose escalation part

Criteria	eFORM Variables	Control / program (TOL=1)
Toxicity will be graded using the common toxicity criteria from the NCI v4.0.	ADVERSE EVENT FORM AEVENT (adverse event) AESAE (is a serious adverse event) AE_NUMAE (Toxicity number) DT_SAE , DT_AE (date of beginning) DTENDAE (date of the end or death) INIT_INT, MAX_INT (intensity) TRAB_REL (relation to Trabectedin) DURV_REL (relation to Durvalumab) AE_TRA_MOD (Trabectedin modification) AE_DUR_MOD (Durvalumab modification) AE_OUTC (outcome)	Listing of Adverse events + descriptive statistics
Incidence rate of DLT will be reported at each dose level on cycle 1.	CYCLE 1 – TREATMENT DOSE_TRA DOSE-LIMITING TOXICITY FORM DT_EVENT OCC_CYC (occurred for the first 21 days) GR4_TOX GR3_NHT GR3_HT GR3_NEU GR2_THR OTH_DLT	Listing Of DLT + rate of DLT (Number of DLT / TOL) descriptive statistics

- Expansion cohorts

Criteria	eFORM Variables	Control (TOL=1)
Objective response rate, defined as the rate of complete or partial response according to RECIST v1.1	ASSE_CYC (TUMOR ASSESSMENT) DT_MEASC (date of measurement) ME1RTLC-ME5 RTLC (measures of lesions) SUM_RTLC (largest diameters) EVA1RLNMC-EVA5 RLNMC (non-measurable lesions eval) RES_RTLC, RES_RNTLC (target and non-target lesions) OV_REV (overall response) CR=1, PR=2, SD=3, PD=4, NE=5 New variables : NB_BORR (nb of objective response case) END OF STUDY (END_STU) DT_EOS (date of end of study)	Status at each TUMOR ASSESSMENT

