3.2. DEFINITIONS

Dose-limiting toxicity (DLT):

A DLT is defined as an AE or laboratory abnormality that fulfills all the criteria below:

- Begins on the first 21 days of treatment.
- Is considered to be at least possibly related to the study treatment.
- Meets one of the criteria below, graded as outlined or according to NCI-CTCAEv4.03 :
 - Any grade-4 toxicity (except for vomiting without maximal symptomatic/prophylactic treatment and if toxicity is transaminitis, but which have to be resolved at Day 21, i.e. return to Baseline or grade 1).
 - Grade-3 non-haematological toxicity lasting > 7days (except for 1rst episode of nausea and if toxicity is transaminitis, which have to be resolved at Day 21, i.e. return to Baseline or grade 1).
 - Grade-3 hematologic toxicity lasting for > 7days.
 - Grade 4 neutropenia with fever.
 - Grade > 2 thrombocytopenia with bleeding.

DLT status:

In addition, the steering committee will resolve any specific issue regarding the DLT status (see section 12.1.1).

Maximum tolerated dose (MTD):

The MTD is defined as the highest dose at which no more than 1 in 6 patients in the cohort experience a DLT in the first 21 days. The conclusions of the steering committee for the definition of

of the MTD will be submitted for approval to an independent data monitoring committee (IDMC) before opening the expansion cohorts.

Recommended phase II dose (RP2D):

The RP2D dose corresponds to the dose level to be recommended for further investigations in phase II trials. The RP2D dose for trabectedin when given in combination with Durvalumab, will be identified by the steering committee based on safety data from patients included in the dose escalation part and the expansion cohorts, as well as PD data. Data from all patients (dose escalation trial and expansion cohorts) will be used to define the RP2D.

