3.3.2. Dose levels

Dose escalation study assessing 3 doses level of Trabectedin given in combination with durvalumab (fixed dose).

Level	-1	1	2	3
Trabectedin (3h)	0.8 mg/m ²	1 mg/m ²	1.2 mg/m ²	1.5 mg/m ²

- The starting dose of Trabectedin is 1 mg/m².
- The maximum dose of Trabectedin administered (1.5 mg/m²) will not be exceeded.
- Patients will be allocated to 3 doses levels following a 3 + 3 design.
- A minimum of 3 patients and a maximum of 6 patients will be entered on each dose level.
- All 3 patients within a dose level will be observed during 21 days (the period of observation of DLTs) before accrual to the next higher dose level may begin.
- Dose escalation will proceed according to the following scheme:

Number of patients with DLT at one dose level	Escalation Decision Rule
0 out of 3	Enter 3 patients at the next dose level.
≥2	Dose escalation will be stopped. This dose level will be declared as the maximum administered dose (MAD). Three additional patients will be entered at the next lowest dose level if only 3 patients were treated previously at that dose.
1 out of 3	Enter at least 3 more patients at this dose level. 
• If 0 of these 3 patients experience DLT, proceed to the next dose level.• If 1 or more of this group suffer DLT, dose escalation will be stopped, and this dose is declared as the MAD. Three additional patients will be entered at the next lowest dose if only 3 patients were treated previously at that dose.
≤1 out of 6	This will be the maximum tolerated dose (MTD).

- As described above, the maximum administered dose (MAD) for Trabectedin is the dose in which ≥2/3 or ≥2/6 patients experience DLT.

- If the MAD for Trabectedin is seen at the starting dose level, then dose level “-1” will be the recommended dose.
- The MTD for Trabectedin is defined as the highest dose at which no more than 1 in 6 of the patients in the cohort experienced a DLT during the period of observation of DLTs.
- The steering committee will meet before proceeding or not to each dose escalation. In addition, the steering committee will be consulted to resolve any specific question regarding the DLT status (see section 12.1.1).
- Conclusions of the steering committee for the definition of MTD will be submitted for approval to an independent data monitoring committee (IDMC) before opening the expansion cohorts.

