9. STATISTICAL CONSIDERATIONS

9.1. Hypotheses and number of subjects needed

9.1.1. Phase I (Dose escalation part)

- 3 dose levels
- A minimum of 3 patients will be entered in each dose level
- A maximum of 6 patients will be entered in each dose level

Therefore, the maximum number of patients is estimated to be 18 patients assessable for safety. To account for patients not assessable, we anticipate accruing a maximum of **20 patients for the dose escalation part of the phase I trial**.

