11. QUALITY ASSURANCE AND TRIAL MONITORING

11.1. Monitoring of the trial

11.1.1. *Steering Committee*

The study will be supervised and monitored by a steering committee comprising members participating in the study:

- Dr. [name], Coordinating Investigator and Chairman of the committee.
- Dr. [name], Scientific responsive, medical oncologist.
- A representative of the sponsor (Pr [name] or a substitute).
- The biostatistician of the trial (Ms. [name], or a substitute).
- The pharmacist of the trial (Ms. [name], or a substitute).

This committee must ensure the following:

- Implementation and regular follow-up of the study
- Patient protection,
- That the trial is conducted ethically, in accordance with the protocol,
- That the trial benefit/risk ratio is evaluated and the scientific results are checked during or at the end of the trial.

For the dose escalation part, the steering committee will be consulted before proceeding or not to the next dose level.

In addition, the steering committee will resolve any specific issue regarding the DLT status. Note however, that medical oncologists of the steering committee cannot comment on the DLT status of patients they have been in charge of. In such case, the opinion of another medical oncologist who has not treated the patient will be sought.

The steering committee decides on any relevant amendment to the protocol that is required in order to continue the trial (protocol amendments prior to submission to the EC and the relevant Health Authorities, decisions on whether to open or close research sites, discussion of results and the strategy for the publication of these results). It must inform the sponsor of any decisions taken. Decisions concerning a major amendment or a change to the budget must be approved by the sponsor.

11.1.2. *Independent Data Monitoring Committee*

- An independent data monitoring committee (IDMC) will be created at the request of the relevant Authority, the sponsor or the steering committee. The IDMC plays an advisory role for the Sponsor, who has the final decision regarding the implementation of recommendations put forward by the IDMC.
- Conclusions of the steering committee for the MTD definition based on the dose escalation trial will be submitted for approval to the IDMC before opening the expansion cohorts. If necessary, a second IDMC may be set up at the end of the expansion cohorts.

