2.3 Dose escalation part/ Assessable for safety

The following patients will not be included in the population assessable for safety (primary analysis) and thus will be replaced:

- Patients who received $\leq 75\%$ RDI (Relative Dose Intensity) for trabectedin OR $\leq 75\%$ RDI for durvalumab over cycle 1, due to drug-related AE not considered as DLT.
- Patients who goes off treatment over cycle 1 for reasons unrelated to toxicity (DLT or any other AE), e.g. progression, lost to follow-up, will be replaced.

Population assessable for safety (primary analysis): all patients who completed the DLT assessment period or who developed DLT are included in the analysis.

CREATION OF A NEW INDICATOR VARIABLE

New binary variable TOL

Label: « Assessable for Safety»

TOL = 1 if the patient is assessable for safety (primary analysis)

TOL = 0 if the patient is not assessable for safety (primary analysis)

Criteria	eFORM variable	Control / program
Patient received $\leq 75\%$ RDI (Relative Dose Intensity) for trabectedin OR $\leq 75\%$ RDI for durvalumab over cycle 1, due to drug-related AE not considered as DLT	CYCLE 1 – DAY 1 AND DAY 2 (WEEK1) TREATMENT Trabectedin DOSE_TRA (dose) VPRE_TRA (volume of preparation) VOL_TRA (administered volume) WHY_TRA (2=AE related to treatment) Durvalumab DOSE_DU VPRE_DU VOL_DU WHY_DU DOSE-LIMITING TOXICITY FORM DLT_CYC OCC_CYC REL_ST	IF Trabectedin $((\text{Dose effectivement reçue VPRE_TRA and VOL_TRA/DOSE_TRA}) \leq 75\% \text{ AND INT_TRA} = 1 \text{ AND WHY_TRA} = 2 \text{ AND DLT_CYC} = 0)$ OR Durvalumab $((\text{Dose effectivement reçue VPRE_DU and VOL_DU / 1120 mg}) \leq 75\% \text{ AND INTER_D} = 1 \text{ AND WHY_DU} = 2 \text{ AND DLT_CYC} = 0)$ THEN TOL = 0
Patient goes off treatment over cycle 1 for reasons unrelated to toxicity (DLT or any other AE), e.g. progression, lost to follow-up	DISCONTINUATION VISIT END OF TREATMENT / end of treatment form DT_SOT DT_EOT EOTREASO DISCONTINUATION VISIT END OF TREATMENT / visit DIS_TRT TRA_EOT DUR_EOT DOSE-LIMITING TOXICITY FORM DLT_CYC AE FORM NUMAE AEVENT DT_AE MAX_INT TRA_MOD DUR_MOD	$\text{DT_EOT-DT_SOT} \leq 21 \text{ days}$ AND EOTREASO NOT IN (4 12) AND DLT_CYC=0 Additional control if $\text{DT_EOT-DT_SOT} \leq 21 \text{ days}$ 
 - Listing Other reason - Listing visit of end of treatment: DIS_TRT / TRA_EOT / DUR_EOT - Listing AE with TRA_MOD IN=3 OR DUR_MOD=3 THEN TOL=0

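### The only DLT rate planned at the MTD comes from the escalation patients who selected that dose, so it is biased low and has no confidence interval; the expansion patients give no DLT estimate, although the RP2D is to use all patients

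*SAP*

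**What the plan says.** The primary objective (Protocol 2.1) covers the RP2D, the MTD, the safety profile and the DLTs. On the data behind the RP2D, Protocol 3.2 is explicit: "Data from all patients (dose escalation trial and expansion cohorts) will be used to define the RP2D". Protocol 3.4 repeats this. Protocol 3.3.2 defines the MTD as the "highest dose at which no more than 1 in 6 of the patients in the cohort experienced a DLT".

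For the DLT endpoint, the SAP specifies the following.

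- Section 3.2.1 analyses the primary endpoint on the escalation part's safety-assessable population.
- Section 2.3 defines that population, flag TOL, for the escalation part only: "Population assessable for safety (primary analysis): all patients who completed the DLT assessment period or who developed DLT are included in the analysis".
- Section 3.2.3, under the dose escalation part, says "Incidence rate of DLT will be reported at each dose level on cycle 1" and gives the calculation as the number of DLTs divided by TOL. The expansion table in the same section contains objective response only.
- The list of tables in section 4.3 has no DLT table for either part.
- No confidence interval is named for the DLT rate. Section 3.1 offers standard errors for categorical endpoints in general.

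For expansion safety, SAP 3.2.2 plans an analysis of all treated patients, with 95% binomial intervals for qualitative variables. Protocol 8.2 lists toxicity as an expansion secondary endpoint, defined as in the escalation part. Independent review after expansion is optional: "If necessary, a second IDMC may be set up at the end of the expansion cohorts".

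**The concern.** An estimate taken from the same patients who qualified the dose is subject to selection. Had those patients shown two or more DLTs, the dose would not have been called the MTD, so unfavourable results are removed before the rate is reported. With six patients the remaining figure is also very imprecise, and without an interval a reader cannot see this.

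The expansion patients are enrolled after the dose has been fixed, at the same dose and on the same schedule. Their DLT rate would be free of this selection and based on about five times as many patients. The plan says that their data help to set the RP2D but specifies no DLT estimate from them. The steering committee could then set the RP2D, and the trial could report a DLT rate for it, from a figure that tends to look better than the truth.

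**Working it through.** **Inputs.** Protocol 3.3.2: "A minimum of 3 patients and a maximum of 6 patients will be entered on each dose level". Protocol 9.1.1 (dose escalation part): "the maximum number of patients is estimated to be 18 patients assessable for safety". Protocol 9.1.1 (expansion cohorts): 15 patients recruited per cohort, 30 in total, all at the MTD. The documents give no target or unacceptable DLT rate, so I show a range of true rates. I assume six assessable escalation patients at the MTD and independent outcomes.

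**The plan's own figure.** 3 levels × 6 patients = 18, as stated. Six is therefore the most that the escalation part can supply at the MTD.

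**Selection.** Let p be the true 21-day DLT rate and X the number of the six patients with a DLT.

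- P(X ≤ 1) = (1−p)^6 + 6p(1−p)^5.
- Mean observed rate given X ≤ 1 = [6p(1−p)^5 / P(X ≤ 1)] / 6.

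| True rate p | P(X ≤ 1 of 6) | Mean observed rate given X ≤ 1 |
|---|---|---|
| 20% | 65.5% | 10.0% |
| 25% | 53.4% | 11.1% |
| 30% | 42.0% | 12.0% |
| 1/3 | 35.1% | 12.5% |
| 40% | 23.3% | 13.3% |

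For p = 1/3: (0.0878 + 0.2634) = 0.351, and (0.2634/0.351)/6 = 0.125. The reported rate hardly moves while the true rate doubles from 20% to 40%.

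**Precision with six patients (exact 95% limits).** 0/6: 0% to 45.9%. 1/6: 0.4% to 64.1%. The standard error in SAP 3.1 does not replace these limits: for 1/6 it is √[(1/6)(5/6)/6] = 15.2 points, and for 0/6 it is zero.

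**What the expansion patients would add.** The counts are illustrative, since the documents give none.

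- Both cohorts together, 5/30: 5.6% to 34.7%.
- One cohort, 2/15: 1.7% to 40.5%.
- Pooled with escalation, 6/36: 6.4% to 32.8%. This interval takes no account of the selection in the six escalation patients.

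At p = 1/3, the chance of 5 or fewer DLT patients in 30 is 3.5%, against 35.1% for at most 1 in 6.

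**Pooling keeps part of the selection.** At p = 1/3, treating all 36 as unselected gives P(6 or fewer) = 2.2%. That is not the relevant figure, because the six escalation patients are known to have had at most one DLT. Given X ≤ 1, X is 0 with probability 0.0878/0.351 = 0.25 and 1 with probability 0.75. The chance is then 0.25 × P(Y ≤ 6 of 30) + 0.75 × P(Y ≤ 5 of 30) = 0.25 × 0.0838 + 0.75 × 0.0355 = 4.8%.

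**The case against.** The strongest reply is that tolerability at the MTD does not rest on six patients. A reader might infer that it does, and the documents do not support that. The RP2D draws on expansion safety data and pharmacodynamic data as well. Expansion safety is analysed on all treated patients with binomial intervals (SAP 3.2.2). SAP 3.1 allows combined analyses of all study patients. The expansion listings give onset, maximum intensity, relatedness and end date, so the committee can see severe related events in cycle 1. This stands, and it confines the point to the DLT rate.

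It does not close the gap. Summaries by system organ class do not apply the DLT definition, with its 21-day window, relatedness, duration criteria and transaminitis exception. In addition, Tables 11.1 and 12.1 are specified for patients assessable for efficacy, which does not match the safety population named in SAP 3.2.2. It could be argued that toxicity defined as for escalation (Protocol 8.2) includes DLT incidence. That is unclear, and no SAP output follows from it.

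Two further objections stand. SAP 3.2.2 analyses the two tumour types separately, so a combined expansion estimate needs results by cohort beside it, and the cohort intervals are wide. It is also not shown that the expansion part captures everything the definition needs. The grade-change listing belongs to the dose-level reports in Appendix 1, expansion Datalisting 6.1 gives initial and maximum intensity only, and the documents do not say whether the DLT form is completed there.

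**Conclusion.** The point holds for the DLT rate at the MTD. That rate is planned from escalation patients only and without a confidence interval. Where the 3+3 rule sets the MTD, the proportion of patients with a DLT cannot exceed 1/6 and is biased low: 10% on average when the truth is 20%, and 12.5% when it is one third. The exact interval for 1/6 runs from 0.4% to 64%.

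Two limits apply. First, a reader might infer that the reported rate can never exceed 1/6. The documents do not support that. SAP 3.2.3 divides the number of DLTs, not patients, by TOL, so one patient with two DLTs could push the ratio higher. If the starting level proves to be the maximum administered dose, a fallback rule applies with no stated DLT count. The protocol synopsis and Protocol 3.3.2 name different levels for that fallback, and the two passages must be reconciled. Second, one third is my benchmark and not the trial's; the downward bias appears at every rate in the table.

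The escalation design is not in question. This is a worthwhile, low-cost addition, because it supplies the one selection-free estimate of a quantity in the primary objective.

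**What to change.** Change the SAP only, in 3.2.2, 3.2.3 and the list of tables.

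1. Apply the existing DLT definition to the first 21 days of expansion patients, with a DLT-assessable flag defined as in SAP 2.3.
2. Report patients with a DLT divided by assessable patients, not the number of DLTs, with exact 95% confidence intervals:
   - (a) expansion patients alone, both cohorts together as the main selection-free estimate, and by cohort in line with SAP 3.2.2;
   - (b) pooled with the escalation patients treated at the MTD, labelled as still partly affected by selection.
3. Give the steering committee this table for the RP2D decision.

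No protocol change is needed, since Protocol 3.2 and 3.4 already call for data from all patients.

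The cost is SAP wording and one table, with no added patients. The sponsor must confirm that the DLT form, or dated grade changes, are captured in the expansion part; if they are not, some durations will have to be queried. The steering committee would also have to rule on unclear DLT status in expansion patients. The denominator may fall below 30, because the SAP 2.3 rule removes some patients with reduced cycle 1 dosing or early withdrawal. The stated DLT rate may also look less favourable.
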